3.5.3 Vital Signs

Vital signs will include systolic and diastolic blood pressure, heart rate, temperature and respiratory rate. Descriptive statistics will be provided for vital sign values as well as change from baseline at each scheduled visit.

3.5.4 Electrocardiograms

For the continuous variables, descriptive statistics of results at each study visit, as well as the change from baseline to each study visit, will be presented in summary tables; for the categorical responses to overall interpretation (rhythm), results and the associated findings at each visit will be summarized by counts and percentages.

Number and percentage of patients with QTcF interval in the categories below will be provided.

- Absolute QTcF interval >500 msec,
- Absolute QT interval >500 msec,
- Increase from baseline QTcF interval >60 msec.

A shift table from baseline to scheduled post-baseline will be tabulated for overall interpretation (rhythm).

3.5.5 Injection Site Assessments

The number and percentage of subjects will be presented for any pain, tenderness, erythema/redness, and induration/swelling of injection site location at each visit and time point.

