5. STUDY POPULATION

5.1. Participants

In this trial the inclusion of a high-risk population defined by coronary artery calcification (inclusion criterion 4g) offers an opportunity to investigate the effect of Lp(a)-lowering treatment in a group of patients with at least a \times 2-fold increase risk of ASCVD as demonstrated in the Multi-Ethnic Study of Atherosclerosis (MESA) and Dallas Heart Study [[Mehta et al, 2022](#)]. As GalNAc siRNA is a highly targeted approach there are no anticipated differences in safety and efficacy that will be evaluated in this study in the proposed broad population¹

Approximately 160 participants are planned to be recruited at approximately 40 centres worldwide. Each placebo group will include 20 randomly allocated participants, and each SLN360 group will include 40 randomly allocated participants. This will result in a total of 120 participants exposed to SLN360 and 40 participants exposed to placebo.

The number of participants assigned to each treatment group is summarised in [Table 5](#).

Table 5 Treatment groups and planned number of participants

Group	N	Planned dose	Dosing regimen	Total participants
1	20	Placebo	Q16W	160 (120 SLN360, 40 placebo)
2 ^a	20	Placebo	Q24W	
3	40	SLN360 300 mg	Q16W	
4	40	SLN360 300 mg	Q24W	
5	40	SLN360 450 mg	Q24W	

Q16W=dosing every 16 weeks; Q24W=dosing every 24 weeks

a. Group 2 will be stratified so that half of participants receive 1.5 mL placebo (to match the volume of the 300 mg SLN360 dose) and half receive 2.25 mL placebo (to match the volume of the 450 mg SLN360 dose)

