8. INVESTIGATIONAL PRODUCT(S)

8.1. Dosage and Administration

SLN360 is provided as a solution for injection for subcutaneous use in glass vials. A vial (2R vial) contains 0.5 mL (extractable volume) of an aqueous sterile solution of SLN360 drug substance with a concentration of 200 mg/mL (as free acid form). The vials are intended for single use. SLN360 will be supplied by the Sponsor or designee, along with the batch/lot numbers and Certificates of Analysis.

Each dose of SLN360 or placebo will be administered via subcutaneous injection by appropriately qualified clinical study site staff. The injection will be delivered in the abdomen, avoiding areas where the skin is red, bruised, tender, indurated or in sites of previous scars. Where other medicinal products are required to be given by subcutaneous administration, these should be administered preferably at different sites.

Study Number: SLN360-002	Compound No.: SLN360
Protocol	Version: 1.0

Individual injection volume at each injection site will not exceed 1.5 mL, and up to two injection sites may be used to achieve the required dose. Please refer to the IMP Handling Manual for further guidance.

Where multiple injections are required in one dosing session, injection sites ideally should be separated by a few centimetres, according to local practice. When multiple injections are given, injection sites should be rotated to a different location (i.e., not administered in precisely the same place for subsequent administrations) and a new quadrant of the abdomen should be used for each injection. It is recommended to proceed around the quadrants in a clockwise direction. Injection sites should be recorded in the eCRF.

Participants will be dosed at the timepoints outlined in the Time and Events tables ([Appendix 15.1](#) and [Appendix 15.2](#)).

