2.2.1 Overview

The study will be divided into three study periods, comprising screening, treatment and follow-up. An end-of-study visit will be conducted to perform final safety and efficacy assessments.

Eligible participants will receive either placebo or SLN360 and will be randomised in the ratio 1:1:2:2:2 into five treatment groups:

- Group 1: Placebo administered subcutaneously at Weeks 0, 16 and 32 (dosing every 16 weeks [Q16W])
- Group 2: Placebo administered subcutaneously at Weeks 0 and 24 (dosing every 24 weeks [Q24W])
 - This group will be stratified so that half of participants are dosed to match the 300 mg Q24W SLN360 group and half are dosed to match the 450 mg Q24W SLN360 group (with respect to injected volume)
- Group 3: SLN360 300 mg administered subcutaneously at Weeks 0, 16 and 32(Q16W)

- Group 4: SLN360 300 mg administered subcutaneously at Weeks 0 and 24 (Q24W)
- Group 5: SLN360 450 mg administered subcutaneously at Weeks 0 and 24 (Q24W)

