3.5 Safety Assessment

All safety data will be included in the subject data listings. Safety data will be summarised by actual treatment received (and in total for selected analyses) based on the Safety Population.

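### Group 2 is split by injected volume to match the two Q24W doses, but no planned injection-site table uses the split

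*SAP*

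**What the plan says.** **Design.** Footnote a to Protocol Table 5 (section 5.1) divides Group 2 by volume. For the lower volume it says: "half of participants receive 1.5 mL placebo (to match the volume of the 300 mg SLN360 dose". The remaining participants are the counterpart of the higher dose: "half receive 2.25 mL placebo (to match the volume of the 450 mg SLN360 dose". SAP 2.2.1 restates the split in its design overview: "This group will be stratified so that half of participants are dosed to match the 300 mg Q24W SLN360 group and half are dosed to". That sentence then names the higher-dose Q24W arm as the other counterpart. Protocol 8.1 limits the volume per site: "Individual injection volume at each injection site will not exceed 1.5 mL, and up to two injection sites may be used". SAP 2.2.3 has the same limit.

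**Analysis.** SAP 3.5.5 is one sentence, and it covers visits and time points within visits: "The number and percentage of subjects will be presented for any pain, tenderness, erythema/redness, and induration/swelling of injection site location at each visit". The grouping comes from SAP 3.5: "Safety data will be summarised by actual treatment received (and in total for selected analyses) based on the Safety Population". SAP Table 1 lists placebo Q24W as a single regimen. SAP 2.2.4 reports the two placebo groups separately and combined, and does not mention a split by volume. SAP 3.3.7 summarises volume and number of injections by treatment, as exposure only. SAP 3.5.1 tabulates treatment-emergent adverse events (TEAEs) by treatment, also without the volume stratum.

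**The concern.** The two Q24W active arms differ in drug dose, in volume and, on the stated limits, in the minimum number of injection sites per dose. The volume-matched halves of Group 2 are the only randomised control that holds volume fixed while removing the drug. In the planned tables those halves are merged, so half of the placebo column has the wrong volume for Group 4 and the other half has the wrong volume for Group 5.

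Local tolerability matters in this trial. Protocol 6.5.2 gives injection site reactions their own assessment and grading. Protocol 1.3 reports low-grade injection site events as the most common adverse events in the single-dose Phase 1 data. Protocol 8.2.1 cites such reactions among the reasons for not pursuing 600 mg. The trial's aim includes finding a regimen with favourable tolerability, so readers will compare 300 mg with 450 mg at the injection site.

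**Working it through.** **1. The plan's own figures.** At 200 mg/mL, 300/200 = 1.5 mL and 450/200 = 2.25 mL, which agrees with the matching volumes. At most 1.5 mL per site, 1.5 mL needs at least one site and 2.25 mL at least two. Allocation 1:1:2:2:2 of 160 gives 160 × 1/8 = 20 and 160 × 2/8 = 40. Half of Group 2 is 10.

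**2. Assumptions not in the documents.** Let p be the probability of a sign per injection and ρ the correlation between two sites in one person. Neither is given, so both are varied. The drug has no effect, volume acts only through the number of injections, and 1.5 mL is given as one injection.

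**3. One dosing visit.**
- One injection (Group 4): p.
- Two injections (Group 5): p₂ = p + p(1 − p)(1 − ρ).
- Undivided Group 2: (p + p₂)/2.
- Distortion: Group 5 up, and Group 4 down, by (p₂ − p)/2 = p(1 − p)(1 − ρ)/2.

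At p = 5%, ρ = 0: p₂ = 9.75%, Group 2 = 7.375%, distortion 2.4 points. At p = 10%, ρ = 0: p₂ = 19%, Group 2 = 14.5%, distortion 4.5 points.

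| p | ρ = 0 | ρ = 0.5 | ρ = 1 |
|---|---|---|---|
| 2% | 1.0 | 0.5 | 0 |
| 5% | 2.4 | 1.2 | 0 |
| 10% | 4.5 | 2.25 | 0 |
| 20% | 8.0 | 4.0 | 0 |

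**4. Any-time incidence, independent injections.** The formula is 1 − (1 − p)^k, with k = 2 in Group 4, k = 4 in Group 5, and half of Group 2 at each.
- p = 5%: 9.8%, 18.5% and 14.1%, a distortion of 4.4 points each way.
- p = 10%: 19.0%, 34.4% and 26.7%, a distortion of 7.7 points each way.

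**5. Scale.** One Group 2 participant is 1/20 = 5 points. At ρ = 0 the standard error of Group 5 minus undivided Group 2 at one visit is 7.5 points at p = 5% and 10.0 at p = 10%, so the per-visit distortion is below one standard error.

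**6. Matched halves.** Group 4 against the 1.5 mL half is p − p = 0, and Group 5 against the 2.25 mL half is p₂ − p₂ = 0, for any p and ρ. The standard error for Group 5 rises to 10.5 points at p = 5% and 13.9 at p = 10%, because only 10 controls remain.

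**7. Why Group 1 should not be added to the 1.5 mL half for any-time incidence.** Group 1 has three doses and Group 4 has two. At p = 5%, assuming 1.5 mL in Group 1, the 30 pooled participants expect [20 × (1 − 0.95³) + 10 × (1 − 0.95²)]/30 = 12.8%, against 9.8% in Group 4. That would be a new mismatch of 3.0 points.

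**The case against.** The strongest counter-argument is accuracy. If the matched display replaced the planned one, total error for Group 5 would grow. At p = 5%, root mean squared error per visit is √(2.4² + 7.5²) ≈ 7.8 points against undivided Group 2, and 10.5 points against the matched half. This stands against replacing the planned tables. It does not stand against adding a second display.

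Four stronger readings are tempting, and the documents do not support them.
- **That 450 mg will show a spurious excess.** This needs reactions to rise with volume or with a second injection, and the documents report neither. If 2.25 mL is divided evenly, each site receives 2.25/2 = 1.125 mL, less than a single 1.5 mL site, which could work the other way.
- **That the split was made to remove confounding of reactions.** Both documents say only that placebo is matched on volume. Keeping the blind is an equally natural purpose.
- **That the number of injections is ignored.** SAP 3.3.7 tabulates it. It is just not related to reactions.
- **That reactions are shown only per visit.** Under Protocol 6.5.2, those meeting adverse event criteria are recorded as such, and SAP 3.5.1 counts subjects and events over the study. Those tables also lack the volume split.

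It is also fair to say that differing dosing visits are handled by reporting the placebo groups separately, that safety is descriptive with no tests (SAP 3.1.6), and that Protocol 11.1.2 names no adverse event of special interest.

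**Conclusion.** The point holds in conditional form. The trial allocates a volume-matched placebo for each Q24W arm, and no planned injection-site or TEAE table uses it. If volume or number of injections matters, the undivided column can flatter 300 mg and disadvantage 450 mg. Under independence that is 2.4 to 4.5 points per dosing visit, and 4.4 to 7.7 points any-time, for p of 5% to 10%. Per visit it shrinks with within-person correlation, and it is zero if neither volume nor a second injection matters.

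The sizes rest on an assumed reaction rate and on 1.5 mL being one injection, which the protocol leaves to the IMP Handling Manual. The gap affects interpretation of descriptive tables. It does not show that any planned conclusion is wrong. It is a cheap improvement.

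**What to change.** Keep the planned tables. In SAP 3.5.5, and for injection-site TEAEs in SAP 3.5.1, add a descriptive display with these pairings:
- Group 4 beside the 1.5 mL half of Group 2.
- Group 5 beside the 2.25 mL half of Group 2.
- Group 3 beside Group 1, after confirming Group 1's volume, which the documents do not state.

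For each, give any-time incidence per participant and reactions per injection given. If 1.5 mL is one injection, including in Group 1, planned injections are 20 × 3 = 60 in Group 1, 10 × 2 = 20 and 10 × 4 = 40 in the halves of Group 2, 40 × 3 = 120 in Group 3, 40 × 2 = 80 in Group 4 and 40 × 4 = 160 in Group 5. Do not pool Group 1 with the 1.5 mL half for any-time incidence. State whether findings are recorded separately for each site when two are used, because the SAP's reference to location leaves this open and the per-injection rate depends on it.

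The cost is one or two extra tables. With 10 participants per placebo stratum one event is 10 points, so intervals will be wide and the display should be labelled descriptive.

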3.5.6 Physical Examinations

A listing of physical examination assessments will be provided.

3.5.7 Other Safety Assessments

All other safety assessments will be listed.

4 INDEPENDENT DATA MONITORING COMMITTEE

The Independent Data Monitoring Committee (IDMC) is responsible for review of data during the study. The IDMC will review accrued data on an ongoing basis and make relevant recommendations to the Sponsor. The IDMC is an independent group of experts in clinical trials, clinical medicine and drug

safety. The details of the role, remit and responsibility of the IDMC, together with practical considerations for data review and IDMC meetings are provided in the IDMC Charter.

5 INTERIM ANALYSIS

There will not be a formal interim data analysis. The database will be locked and the primary analysis will be performed after all participants have completed 36 weeks of treatment. Similar analysis will also be performed after all participants have completed 48 weeks of treatment (end of treatment period). All follow-up data collected up to Week 60 will also be analysed and reported (final analysis).

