4. STUDY DESIGN

4.1. Summary of Study Design

4.1.1. Study Design

This is a multi-centre, randomised, double-blind, placebo-controlled Phase 2 study to investigate the efficacy, safety and tolerability of SLN360 in participants with elevated Lp(a) at high risk of ASCVD.

The study will be divided into three study periods, comprising screening, treatment and follow-up. An end-of-study (EoS) visit will be conducted to perform final safety and efficacy assessments.

Eligible participants will receive either placebo or SLN360 and will be randomised in the ratio 1:1:2:2:2 into five treatment groups:

- Group 1: Placebo administered subcutaneously at Weeks 0, 16 and 32 (dosing every 16 weeks [Q16W])
- Group 2: Placebo administered subcutaneously at Weeks 0 and 24 (dosing every 24 weeks [Q24W])
 - This group will be stratified so that half of participants are dosed to match the 300 mg Q24W SLN360 group and half are dosed to match the 450 mg Q24W SLN360 group) with respect to injected volume
- Group 3: SLN360 300 mg administered subcutaneously at Weeks 0, 16 and 32 (Q16W)
- Group 4: SLN360 300 mg administered subcutaneously at Weeks 0 and 24 (Q24W)
- Group 5: SLN360 450 mg administered subcutaneously at Weeks 0 and 24 (Q24W)

Placebo

The placebo has been chosen as the control treatment to assess whether any observed effects are treatment-related. The placebo is used since no appropriate active comparator is available; notably, there being no approved pharmacotherapy available that has been shown to yield a clinically meaningful lowering of Lp(a) in people with elevated levels.

Study Number: SLN360-002	Compound No.: SLN360
Protocol	Version: 1.0

Dose groups and treatment regimens are summarised in [Table 4](#).

[figure not shown]
Table 4 Dose groups and treatment regimens for the proposed Phase 2 study

Group	Regimen	No. of SLN360 doses	Total cumulative SLN360 administered
1	Placebo Q16W	-	-
2	Placebo Q24W	-	-
3	SLN360 300 mg Q16W	3	900 mg
4	SLN360 300 mg Q24W	2	600 mg
5	SLN360 450 mg Q24W	2	900 mg

Q16W=dosing every 16 weeks; Q24W=dosing every 24 weeks

An overview of the trial is presented in [Figure 2](#).

Figure 2 Overview of the Phase 2 study

Q16W=dosing every 16 weeks; Q24W=dosing every 24 weeks

Details of all dosing and assessment timepoints are outlined in the Time and Events tables ([Appendix 15.1](#) and [Appendix 15.2](#)).

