4.1.3. Duration of Participant Participation

There are a planned minimum of 15 visits for each participant, including screening. The maximum expected duration of participation for an individual participant will be up to 64 weeks. This includes a screening period of up to 4 weeks, a treatment period of up to 36 weeks and a follow-up period of up to 24 weeks, reaching EoS at Week 60.

Primary analysis will be performed once all participants have completed 36 weeks of treatment.

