6.5. Safety Procedures

6.5.1. Adverse Event Assessments

Information regarding the occurrence of AEs for each participant will be collected from the time a signed and dated ICF for the main study is obtained until completion of the participant's last study-related procedure, which may include contact to follow-up for safety. Adverse events that start from the time the participant signs the main study ICF until treatment administration on Day 1 will be assigned as non-treatment emergent AEs; AEs starting or worsening after treatment administration will be recorded as TEAEs. See the Time and Events tables ([Appendix 15.1](#) and [Appendix 15.2](#)) for detailed timing of assessments. Grading of AEs is outlined in [Section 11.2](#).

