12.4.4.2.1. Adverse events

The verbatim terms used in the eCRF by Investigators to identify AEs will be coded using MedDRA. All reported AEs with onset during the treatment phase will be included in the analysis and will be summarised by treatment group, and these include the following: AEs that have worsened since study entry, TEAEs, study drug-related TEAEs, serious TEAEs, study drug-related serious TEAEs, TEAEs leading to study discontinuation, TEAEs leading to discontinuation of study treatment or TEAEs leading to death. All other AEs will be listed only.

For each AE, the number and percentage of participants who experience at least one occurrence of the given event will be summarised by treatment group. Summaries will be presented overall and also by system organ class and preferred term using MedDRA. TEAEs will also be summarised by severity and relationship classified by System Organ Class and Preferred Term.

Study Number: SLN360-002	Compound No.: SLN360
Protocol	Version: 1.0

The number and percentage of early withdrawals and the corresponding reasons will be tabulated presenting number and percentage of participants for each treatment group.

Summaries, listings, datasets or narratives may be provided, as appropriate, for those participants who die, discontinue treatment due to an AE or experience a severe or serious AE.

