3.1.8 Handling of Dropouts and Missing Data

Missing data will not be imputed unless otherwise specified. Only observed data will be used in the summaries and analyses.

In all listings, missing or incomplete dates should be left as they have been recorded. However, for calculation / sorting / assignation based on dates, the following methods will be used:

- 1) The most conservative approach will be systematically considered (i.e. if the onset date of an AE is missing / incomplete, it is assumed to have occurred during the active phase (i.e. a TEAE for AEs) except if the partial onset date or other data [stop date, ...] indicates differently).
- 2) A missing/incomplete date of medical history or disease diagnosis will be assumed to have occurred before any study treatment.
- 3) If a partial date and the associated information do not allow to state about the assignation to a group / category, all the possible groups / categories will be considered (i.e. an AE could be assigned to several possible doses at event onset according to its partial onset date and stop date. Particularly an AE with missing start date will be assigned to each dose received before its end date.).
- 4) Where this is possible, the derivations based on a partial date will be presented as superior inequalities (i.e.: for an AE started in FEB2004 after the administration performed on 31JAN2004, the days since last dose will be “ ≥ 2 ”, similarly the duration of ongoing AEs or medication will be “ $\geq xx$ ” according to the start and last visit dates).

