3.5.1 Adverse Events (AEs)

All AEs will be coded to system organ class and preferred term using MedDRA. Treatment emergent adverse events (TEAEs) are defined as AEs that start after the first dose of study drug. Severity will be graded according to the National Cancer Institute Common Terminology Criteria for Adverse Events (NCI-CTCAE) on a five-point scale (Grade 1 to 5). Study drug-related AEs are defined as AEs considered by the investigator as having a reasonable possibility of being related to study drug.

An overview of TEAEs will be provided including counts and percentages of subjects (and event counts) with the following:

- Any TEAEs (overall and by maximum severity)
- Any study drug-related TEAEs (overall and by maximum severity)
- Any serious adverse events (SAEs)
- Any serious TEAEs
- Any study drug-related serious TEAEs
- Any TEAEs leading to discontinuation of study drug
- Any TEAEs leading to discontinuation of study
- Any TEAEs leading to death

Summary tables of TEAEs, TEAEs by maximum severity, study drug-related TEAEs, serious TEAEs and TEAEs leading to discontinuation of study drug or study will be provided with the number and percentage of subjects with adverse events and the number of events classified by primary system organ class, and preferred term.

System organ classes and preferred terms will be sorted alphabetically.

For tabulations that include classification by relationship to study drug, TEAEs with missing relationship will be considered related to study drug. For tabulations that include classification by severity, missing severity will be considered as the most severe TEAEs that are not SAEs.

Adverse event listings will be presented by subject, system organ class and preferred term.

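### Do the different end weeks for the treatment period (Week 36 in the protocol, Week 48 in the SAP) leave the adverse event tables undefined?

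*SAP*

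**What the plan says.** **Length of treatment.** Protocol section 4.1.1 sets up the periods: "The study will be divided into three study periods, comprising screening, treatment and follow-up". Section 4.1.3 gives their lengths: "a treatment period of up to 36 weeks and a follow-up period of up to 24 weeks", ending at Week 60. SAP section 5 places the end elsewhere: "Similar analysis will also be performed after all participants have completed 48 weeks of treatment (end of treatment period".

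**Which AEs are tabulated.** Protocol section 12.4.4.2.1: "All reported AEs with onset during the treatment phase will be included in the analysis and will be summarised by treatment group". It then says: "All other AEs will be listed only". SAP section 3.5.1 uses treatment emergence instead: "Treatment emergent adverse events (TEAEs) are defined as AEs that start after the first dose of study drug". Protocol section 6.5.1 is close to this: "AEs starting or worsening after treatment administration will be recorded as TEAEs". For an AE with a missing or incomplete onset date, SAP section 3.1.8 says "it is assumed to have occurred during the active phase (i.e. a TEAE for AEs".

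**How long AEs are collected.** Protocol section 6.5.1 collects them until the participant's last study procedure, and section 11.4 until the last follow-up visit.

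**Analyses and declared changes.** Protocol sections 12 and 12.4.3 plan a main analysis at Week 36 and a later one that takes in the data to Week 60. SAP section 5 has three analyses: Weeks 36, 48 and 60. SAP section 6 declares no change from the protocol.

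**The concern.** Read together, these passages seem to allow three counting windows for AEs: to Week 36 (protocol AE rule with the protocol period), to Week 48 (protocol AE rule with the SAP label) and to Week 60 (SAP definition). If they were equally open, two programmers could produce different treatment-emergent and serious-event tables from the same data. That would matter here, because SAP section 2.2.4 justifies the sample size beyond the efficacy need by a more robust safety evaluation.

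Three further points add to the impression. SAP section 6 lists neither the Week 48 analysis nor any departure from the protocol's AE rule. When the last participant reaches Week 36, earlier participants are already past it, and SAP section 3.1.2 applies no visit window to safety data. Finally, neither the active phase (SAP section 3.1.8) nor completion of study treatment (SAP section 3.3.1) is defined.

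**Working it through.** **1. The protocol's own total.** Screening 4 + treatment 36 + follow-up 24 = 64 weeks, the stated maximum, with end of study at 36 + 24 = Week 60. With treatment to Week 48, follow-up to Week 60 would be 12 weeks; keeping 24 weeks would end the study at Week 72. So the SAP label does not fit the protocol's figures. A likely source of the label is the end of the last dosing interval, since 3 × 16 = 2 × 24 = 48 weeks, but neither document says so.

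**2. What each window would cover.** Target days in SAP section 3.1.2 are 252 (Week 36), 337 (Week 48) and 421 (Week 60). Last doses fall on Day 225 (every 16 weeks) and Day 169 (every 24 weeks).

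| Window ends | Share of 421 days | Days after last dose, 16-weekly | Days after last dose, 24-weekly | Gap |
|---|---|---|---|---|
| Day 252 | 59.9% | 27 | 83 | 56 |
| Day 337 | 80.0% | 112 | 168 | 56 |
| Day 421 | 100% | 196 | 252 | 56 |

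The days outside a Week 36 window are 421 − 252 = 169, or 40.1%. The 56-day difference between regimens is the same in every row. It comes from the dosing calendar, so the choice of window neither creates nor removes it.

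**3. Size if the short windows did apply.** The documents available give no AE rates, so 60-week incidences p of 10%, 30% and 70% are assumed. With a constant onset rate, incidence to week w is 1 − (1 − p)^(w/60). For the front-loaded case, assume half the cumulative hazard falls within 4 weeks after doses (all by about Week 36) and the rest is uniform: 1 − (1 − p)^(0.5 + 0.5w/60).

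| Assumed pattern | To Week 36 | To Week 48 | To Week 60 |
|---|---|---|---|
| Constant | 6.1%, 19.3%, 51.4% | 8.1%, 24.8%, 61.8% | 10%, 30%, 70% |
| Front-loaded | 8.1%, 24.8%, 61.8% | 9.0%, 27.5%, 66.2% | 10%, 30%, 70% |

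The shortfall against Week 60 is 1.9 to 18.6 points for Week 36 and 1.0 to 8.2 points for Week 48. These figures count only if a programmer would in fact use a short window.

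**4. Which window the plan gives.** Protocol section 12 leaves the full analysis details to the SAP. The SAP's AE section defines treatment emergence from first dose, builds its AE tables on it, and mentions neither a treatment period nor Week 48. The upper bound is the end of AE collection (protocol sections 6.5.1 and 11.4). One window results: first dose to last follow-up contact.

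The protocol can be read the same way. Section 6.5.1 splits AEs into those before dosing and those after it. Section 12.4.4.2.1 then names mostly treatment-emergent categories as what is summarised, which leaves the pre-dose events for listing. SAP section 3.1.8 treats the active phase and treatment emergence as one. The Week 36 window needs treatment phase, which the protocol does not define, to mean treatment period. The Week 48 window needs that as well, plus a parenthesis borrowed from the SAP's interim analysis section.

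**5. The Week 36 and Week 48 tables.** AEs could be counted to each participant's own visit or to the data cut-off. Under randomisation, extra time beyond the participant's own visit is expected to be similar across arms. The choice therefore moves the level of the percentages more than the comparison, and the final tables replace both.

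**The case for a change.** The strongest case for a change turns on SAP section 6. If it is true that nothing changed, the protocol's AE rule governs and needs an end day on which the documents disagree. If the SAP's definition governs, section 6 is incomplete. Either way the text is imperfect.

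That stands as a point about the record. The Week 48 analysis is an undeclared addition, and the AE definition is an undeclared departure if treatment phase means treatment period. But protocol section 12 allows changes to be documented in the SAP and/or the study report, and section 12.4.6 requires deviations to be explained in the final report. The omission can be made good there without altering an analysis.

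The interim AE cut and the meaning of completed study treatment are also unwritten in the SAP. SAP section 7 leaves detailed programming specifications to a separate document, which is not available here, so they may be settled there. The exposure formula in SAP section 3.3.7 gives 225/7 = 32.1 weeks and 169/7 = 24.1 weeks. It matches neither period, but it is an explicit first-to-last-injection measure and need not match.

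One real difference sits beside this point: the protocol counts AEs that worsen after dosing, whereas the SAP's definition names only those that start. Protocol section 11.3.1 asks for changes in intensity category to be recorded separately with their own onset dates, which should bring most such events under the SAP rule. Even so, the SAP definition cannot be said to lose no event.

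**Conclusion.** The mismatch is real, but the conclusion drawn from it does not hold. Followed as written, the SAP gives complete descriptive AE tables from first dose to the end of AE collection, and the 169 days after Week 36 are included. The possible shortfall of 1.0 to 18.6 points belongs to windows that the SAP's AE section does not use, and it rests on assumed event rates. Efficacy endpoints are fixed by week, no safety hypothesis is tested, and all safety data are listed.

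What is left is a period label on which protocol section 4.1.3 and SAP section 5 must be reconciled as a matter of record, an analysis missing from SAP section 6, and an AE cut for two earlier reports that analysts will set sensibly. None of these would alter a result or a conclusion. The judgement assumes that the SAP's own definition governs its tables and that the interim cut is applied identically in all arms.
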